Our study will enroll participants with at least two fingernails involved. This will allow us to use placebo in one fingernail of every participant, thus establishing the efficacy of ITA in our study by allowing us to compare placebo to ITA. In addition to efficacy assessments, we will measure changes in quality of life due to the study intervention as an outcome. Quality of life assessments will be done with the NPQ10 assessment, which is a validated assessment tool developed to measure quality of life in nail psoriasis.[14] This tool is included in Appendix B.

All fingernails not treated with placebo will undergo randomization to four groups corresponding to four concentrations of ITA under investigation (2.5, 5.0, 7.5, 10.0 mg/mL). Thus, a participant with five affected fingernails may have a different concentration of ITA used as the study intervention in each fingernail. This approach has been used in studies of ITA in other dermatologic diseases such as alopecia areata. [15] In the cited study, the lesions of subjects with alopecia areata were divided into four quadrants, corresponding to four concentrations of ITA that were injected. We believe this approach will be helpful in comparing the efficacy of different concentrations in the same patient.

SIGNIFICANCE

Psoriasis is a chronic, inflammatory condition that affects millions of people in the United States. Approximately 50% of patients with cutaneous psoriasis have nail involvement; nail psoriasis causes significant pain, and can lead to loss of manual dexterity, therefore impairing the ability to use the hands or perform work. Intralesional triamcinolone acetonide is considered one of the mainstays of treatment for nail psoriasis. By determining the lowest effective concentration of this medication for nail psoriasis, we can minimize side effects for millions of people affected with nail psoriasis worldwide.

OBJECTIVES

The primary objective of this study is to determine the lowest effective concentration of intralesional triamcinolone acetonide in the treatment of nail psoriasis.

The secondary objective is to determine that intralesional triamcinolone acetonide is effective in the treatment of nail psoriasis when compared to placebo, using the Nail Psoriasis Severity Index as a measure of improvement.

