Washout Period: Subjects who are using any form of treatment on their nails at the time of the screening visit may participate in the study provided that they are willing to undergo a two-month washout period. During this time, they must abstain from using any nail treatments (including, but not limited to: spa nail treatments, nail polish use, prescribed topical or systemic medications indicated for the nails, over the counter nail treatments, or any other nail intervention with the exception of routine clipping and washing.) After the washout period, the subject may be re-evaluated for participation in the study.

Enrollment and Randomization: Patients with at least two affected fingernails will be enrolled. For each participant, one fingernail will receive an intralesional injection of 0.1-0.2 mL of normal saline (placebo). The other affected fingernail(s) will receive an injection of 0.1-0.2mL of a pre-determined concentration of ITA. Four concentrations of ITA will correspond to four study groups: 2.5mg/mL, 5mg/mL, 7.5mg/mL and 10mg/mL. Participants' fingernails will be randomized such that there are approximately equal numbers of fingernails in each of the five groups (four study interventions, one placebo). To avoid bias, fingernails will be assigned to groups systematically. Fingernails will be assigned to groups in order of anatomical convention. For example, if the subject has involvement of both the thumb, forefinger and third finger of the right hand, the thumb is the first digit, so, if involved, it will be assigned first according to the table below. If a subject has involvement of fingernails of both the right and left hand, the fingernails of the right hand will be assigned before the left. The table assumes that up to 50 nails will be affected between the 10 subjects enrolled. In our clinical experience, this is a reasonable expectation. If more or fewer fingernails are involved during the enrollment period, the randomization table will be adjusted accordingly. The concentration of ITA injected will be different for each group. All other study procedures will be the same between groups.

Fingernail	Group
1	5
2	3
3	4
4	1
5	2
6	4
7	5
8	1
9	3
10	2
11	3
12	4
13	5
14	1
15	2

16	2
17	1
18	3
19	5
20	4
21	5
22	4
23	3
24	2
25	1
26	1
27	2
28	3
29	4
30	5
31	1
32	2
33	4
34	3
35	5
36	5
37	3
38	4
39	2
40	1
41	1
42	3
43	4
44	2
45	5
46	1
47	5
48	2
49	4
50	3

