- Collection of adverse events, if there are any

The following procedures will be performed at the follow-up visit only:

- Measurements of clear nail growth (in millimeters), clear nail area (in mm²)
- Completion of Nail Psoriasis Severity Index.
- Take pictures of subject's nails
- Collection of survey to document subject's changes in quality of life since the beginning of the study intervention and subjective assessment of nail since the beginning of the study intervention

ADVERSE EVENTS AND REPORTING

Adverse event/effect (AE) assessment will be ongoing throughout the study. All adverse events shall be reported by the clinical Investigator to the Sponsor and IRB following WCMC's reporting policies.

Unanticipated Adverse Effect (UAE)

An unanticipated adverse effect is an adverse effect on health and safety caused by, or associated with, the study intervention, if that problem was not previously identified in nature, severity, or degree of incidence in the investigational plan or application, or any other unanticipated problem that relates to the rights, safety, or welfare of subjects.

The Investigator shall be responsible for determination of the causal relationship of all adverse events to the study intervention and/or procedure. The Principal Investigator is responsible for monitoring the safety of the subjects enrolled.

Any adverse events will be reviewed and analyzed by the Principal Investigator as soon as the event occurs and will be documented in the subject's binder. Any unexpected adverse reactions will be reported by telephone to the IRB within 48 hours of observing the event.

No major adverse effects are anticipated during this study; however, we will screen for severe pain (Pain \geq 8/10 on self-reported scale).

The following minor adverse effects are anticipated: cold/burning sensation, minor to moderate pain (Pain \leq 7 on VAS scale), minor swelling (edema), minor hematomas, and temporary erythema (redness). We will screen for additional possible but not expected adverse effects. If the minute treatment reaches an intolerable threshold of pain $>$ 7, the study intervention will be stopped and more anesthetic may be applied if appropriate. Such pain could result from local injection of the skin. A physician will be on site for the to assess for adverse events as needed.

POTENTIAL ADVERSE EFFECTS:	
Epidermal/Nail Response Assessed	Grading
Pain	0 = none 1 2 3 = extreme
Persistent Erythema	0 = none 1 2 3 = extreme

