Skin atrophy	0 = none 1 2 3 = extreme
Bleeding	0 = none 1 2 3 = extreme
Burning/cold sensation	0 = none 1 2 3 = extreme
Hematoma	0 = none 1 2 3 = extreme

Other (please describe and grade, or enter '0' for none)	
--	--

Table 1. The physician shall evaluate the patient's response to the treatment and screen for possible side effects as listed. 0 = none, 1 = mild, 2 = moderate and 3 = extreme.

Photos shall be taken of any visible treatment effects.

EFFICACY EVALUATIONS

The primary endpoint of this study is to assess the lowest effective concentration of intralesional triamcinolone acetonide in the treatment of nail psoriasis. Safety and tolerability shall be determined based on the reported number of adverse events as outlined in the Adverse Events Section and subject-reported symptoms (if any).

In order to evaluate the efficacy of the proposed treatment, high quality photographs will be taken before and after treatment using standardized lighting, exposure settings, and subject positioning. Trained individuals shall assess the changes in the photographs as outlined in the following paragraphs.

Preliminary assessment of the efficacy of the study intervention will be determined by measuring the amount of clear nail growth. This growth will be compared to the initial amount of clear nail recorded at baseline. Changes in clear area and NaPSI will also be reviewed as study intervention progresses and compared to baseline values.

INSTITUTIONAL REVIEW BOARD

Prior to beginning this study, approval for all study related documents (protocol, consent form, advertising) will be obtained from the Weill Cornell Medical College IRB.

DATA ANALYSIS

Efficacy will be evaluated using nail plate measurements to assess clear nail plate growth and rates of clinical improvement. Clinical improvement will be assessed using the NaPSI, an objective validated measuring tool developed by one of the leaders in the field of nail pathology for use in clinical trials on treatment of nail psoriasis.

Adverse effect intensity will be assessed at each of the treatment visits using a 0-3 scale (0=none, 1=mild, 2=moderate, 3=severe) for each side effect with changes from baseline analyzed using the Wilcoxon signed-ranks test and presented as medians and ranges.

Statistical analysis will be performed using SAS version 9.2 (SAS Institute, Cary, NC). Two-tailed $P < 0.05$ will be considered statistically significant.

MONITORING AND QUALITY ASSURANCE

Site Monitoring

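### With one unadjusted P<0.05 and no rule for calling a concentration effective, an inactive drug could yield a lowest effective concentration in about 8% to 20% of trials at the last visit, against a nominal 2.5%

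*Combined protocol and SAP*

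**What the plan says.** All references are to the combined protocol and SAP.

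- **Threshold.** Data Analysis has one rule for every test: a two-tailed P below 0.05 "will be considered statistically significant". No adjustment for multiple tests appears anywhere.
- **Groups.** Enrollment and Randomization: "Four concentrations of ITA will correspond to four study groups: 2.5mg/mL, 5mg/mL, 7.5mg/mL and 10mg/mL". A saline group is the fifth. On size: "The table assumes that up to 50 nails will be affected between the 10 subjects enrolled".
- **Measures.** Data Analysis relies on clear nail plate growth and NaPSI. Efficacy Evaluations adds a third: "Changes in clear area and NaPSI will also be reviewed as study intervention progresses and compared to baseline values". None is called primary.
- **Visits.** Treatment is six-weekly with follow-up at 24 weeks. This implies assessments at about weeks 6, 12, 18 and 24. No visit is named for the decision.
- **Objectives.** The primary objective is to find the lowest effective concentration. The comparison with placebo ranks below it: "The secondary objective is to determine that intralesional triamcinolone acetonide is effective in the treatment of nail psoriasis when compared to placebo", judged by NaPSI.
- **Tests.** The only test named, the Wilcoxon signed-ranks test, is for adverse-effect intensity. No efficacy test is named.

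**The concern.** To name the lowest effective concentration, someone must decide which concentrations are effective. The plan gives no measure, visit, comparator or test for that decision, only a threshold that applies to each test separately. Taken at face value, a concentration could qualify on whichever measure happened to reach P<0.05, and the smallest one to qualify would be the answer. Nothing requires ITA to beat saline first, so a lowest effective concentration could be reported from a trial in which the placebo comparison failed.

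What is at stake is the main conclusion. The stated hypothesis favours the lowest concentration, and choosing the smallest concentration that passes tilts chance findings the same way.

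**Working it through.** The plan states no power or overall error rate to reproduce, so the check asks how often an inactive drug would yield a lowest effective concentration.

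**Inputs from the documents.** Four concentrations and one saline group; 10 participants; up to 50 nails. Counting Table 1 gives exactly 10 nails per group. Two-sided level 0.05, hence 0.05 / 2 = 0.025 per test in the favourable direction. Measures: one (NaPSI), two (Data Analysis) or three (adding clear area). Visits: one or four.

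**Assumed, because the documents do not say.** Any favourable significant result makes a concentration effective. Each participant has five nails, one per group. Each concentration is compared with the participant's own saline nail by a paired t-test (9 df). Data are normal. Within-participant correlation is about 0.5, between-measure correlation 0.5–0.8 and adjacent-visit correlation 0.7.

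**Step 1, bound for independent tests.** The chance of at least one favourable false positive in k tests is 1 − (1 − 0.025)^k.
- 4 tests: 1 − 0.975^4 = 9.6%
- 8 tests (4 × 2 measures): 1 − 0.975^8 = 18.3%
- 12 tests (4 × 3 measures): 1 − 0.975^12 = 26.2%

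**Step 2, simulation with the shared saline nail and correlated measures** (20,000 null trials per setting).

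| Results that can count | False declaration, favourable only | Multiple of 2.5% |
|---|---|---|
| One measure, last visit | about 8% | 8 / 2.5 ≈ 3 |
| Two measures, last visit | 12–14% | 12 / 2.5 ≈ 5 to 14 / 2.5 ≈ 6 |
| Three measures, last visit | 15–20% | 15 / 2.5 = 6 to 20 / 2.5 = 8 |
| Three measures, any of four visits | 37–45% | 37 / 2.5 ≈ 15 to 45 / 2.5 = 18 |

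**Step 3, sensitivity to the unstated test.** Unpaired t-tests that ignore correlation between nails of the same person give lower rates. With three measures the favourable rate is 9.5% at within-participant correlation 0.3 (measures correlated 0.5) and about 4% at 0.5. With one measure it is 3.6% at 0.3. Tests against baseline, with no drift in untreated nails, give 21–24% for three measures at correlations 0.7 and 0.5.

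**Step 4, where the false declarations fall.** With three measures at the last visit, 2.5 mg/mL is named in 34–36% of false declarations, against 25% if the four concentrations were equally likely. In 85–88% of false declarations, pooled ITA versus saline on NaPSI at that visit is not significantly favourable, so a placebo gate would have stopped them.

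**Step 5, effect of a gate.** Testing pooled ITA against saline on NaPSI first lets an inactive drug through in 4.8% of trials in either direction and 2.4% in the favourable direction. No later step in a fixed sequence can be reached without passing this one.

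**The case against.** The strongest reply is that the number of tests is the reviewer's, not the plan's. Data Analysis names two efficacy measures. Clear area is only to be reviewed as treatment proceeds, which is not a commitment to test it, and nothing commits the sponsor to a significance test at each visit. This stands: the three-measure and four-visit rows show what the plan permits, not what it promises. But with one measure at one visit the paired rate is still about three times nominal.

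The simulated layout is also tidier than the protocol's. Participants may have only two affected nails, and Table 1 runs nail by nail across participants. If the first two enrolled had two nails each, the second would receive groups 4 and 1 and no saline, although the text promises every participant a saline nail. This stands too, and it limits the precision of the rates and shapes the fix.

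The ranking of objectives can be defended. The background treats ITA as already shown to work, and the documents set no testing sequence. A reader might infer that the plan tests in the wrong order; it sets only a rank of objectives, and what is missing is a gate.

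Finally, the pull towards 2.5 mg/mL is modest: about one third of false declarations against one quarter. It does not show that the predicted result is built in.

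**Conclusion.** The concern holds: as written, the plan does not control the error rate of its primary claim. An inactive drug would yield a lowest effective concentration at the last visit in about 8% (one measure), 12–14% (two) or 15–20% (three) of trials, and in 37–45% if any of four visits counts. The nominal favourable rate is 2.5%. These figures rest on paired tests, five nails per participant and assumed correlations; unpaired tests that ignore clustering would bring the rate to about 4–10%.

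A reader might infer a chance of one in three at the last visit, or above two thirds over all visits. Those numbers (31–37% and 69–77%) come from counting every two-sided P<0.05, including results where ITA is significantly worse than saline. Such results cannot make a concentration effective, and removing them roughly halves the last-visit figure. Even 12 independent tests give only 26%.

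The root gap is the missing measure, visit, test and decision rule; the inflated error follows from it.

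**What to change.** Add one paragraph to Data Analysis:

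- The single decision measure is change in NaPSI per nail from baseline to week 24.
- Test in fixed order, each step at two-sided 0.05 and passed only if the difference favours ITA, stopping at the first failure: all ITA nails pooled versus saline, then 10, 7.5, 5 and 2.5 mg/mL, each versus saline.
- Use a model with participant as a random effect, so that participants lacking a saline nail or some concentrations still contribute.
- The lowest effective concentration is the last concentration step passed. None is claimed if the pooled step fails, or if it is the only step passed.
- Report other measures and visits with confidence intervals and no significance claim.

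The objectives need not be reordered. No new visits, nails or measurements are needed, and the sequence holds the favourable error at about 2.5%. There are two costs: a chance failure at a higher concentration blocks claims for lower ones, and the pooled step can fail if only the higher concentrations work. Another prespecified procedure on a single measure, such as Dunnett's, would also control the error; what matters is that one is fixed before the data are seen.

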APPENDIX A

Nail Psoriasis Severity Index

Nail Psoriasis Severity Index (NAPSI)

The target nail is graded for nail matrix psoriasis and nail bed psoriasis. The sum of these two scores is the total score for that nail.

Nail Matrix Psoriasis consists of any the following: pitting, leukonychia, red spots in the lunula, and nail plate crumbling.

Score for **matrix psoriasis** 2

- 0=none
- 1=present in 1/4 nail
- 2=present in 2/4
- 3=present in 3/4
- 4=present in 4/4

Nail Bed Psoriasis is the presence or absence of any of the following: onycholysis, splinter hemorrhages, oil drop (salmon patch) discoloration, and nail bed hyperkeratosis.

Score for **nail bed psoriasis** 3

- 0=none
- 1=present in 1/4 nail
- 2=present in 2/4
- 3=present in 3/4
- 4=present in 4/4

Total for nail 5 (0-8)

C

From Rich, P. and R.K. Scher, *Nail Psoriasis Severity Index: a useful tool for evaluation of nail psoriasis*. J Am Acad Dermatol, 2003. **49**(2): p. 206-12.

Table I . Instructions for grading psoriatic nails using NAPSI*

The nail is divided with imaginary horizontal and longitudinal lines into quadrants. Each nail is given a score for nail bed psoriasis (0-4) and nail matrix psoriasis (0-4) depending on the presence of *any* of the features of nail psoriasis in that quadrant.

1. Evaluation 1: Nail matrix. In each quadrant of the nail, nail matrix psoriasis is evaluated by presence of *any* of the nail matrix features (pitting, leukonychia red spots in the lunula, crumbling): 0 for none, 1 if present in 1 quadrant of the nail, 2 if present in 2 quadrants of the nail, 3 if present in 3 quadrants of the nail, and 4 if present in 4 quadrants of the nail.
2. Evaluation 2: Nail bed. Nail bed psoriasis is evaluated by the presence of *any* of the nail bed features (onycholysis, splinter hemorrhages, subungual hyperkeratosis, "oil drop" (salmon patch dyschroma): 0 for none, 1 for 1 quadrant only, 2 for 2 quadrants, 3 for 3 quadrants, and 4 for 4 quadrants.
3. Each nail gets a matrix score and a nail bed score, the total of which is the score for that nail (0-8).
4. Each nail is evaluated, and the sum of all the nails is the total NAPSI score. The sum of the scores from all nails is 0-80; or 0-160 if toenails are included. At any time the matrix or nail bed score can be assessed independently if desired.

If a target nail scale is desired, the same technique can be used to evaluate all 8 parameters (pitting, leukonychia, red spots in lunula, crumbling, oil drop, onycholysis, hyperkeratosis, and splinter hemorrhages) in each quadrant of the nail, giving that 1 nail a score of 0-32.

From Rich, P. and R.K. Scher, *Nail Psoriasis Severity Index: a useful tool for evaluation of nail psoriasis*. J Am Acad Dermatol, 2003. **49**(2): p. 206-12.

APPENDIX B

NPQ10

Directions: Below is a series of statements. Read each statement. Then, circle the answer choice that best describes your experience with nail psoriasis.

1. State the location of your psoriasis of the nails.
 - a. Fingernails
 - b. Toenails
 - c. Both
2. Would you say that your psoriasis of the nails is mostly:
 - a. Very painful
 - b. Somewhat painful
 - c. Not painful
3. Because of my psoriasis of the nails, I have difficulty putting my shoes on.
 - a. Always
 - b. Sometimes
 - c. Never
4. Because of my psoriasis of the nails, I don't do any of the jobs I usually do around the house.
 - a. Always
 - b. Sometimes
 - c. Never
5. Because of my psoriasis of the nails, I get dressed more slowly than usual.
 - a. Always
 - b. Sometimes
 - c. Never
6. Because of my psoriasis of the nails, I have trouble putting on my socks (or stockings or tights).
 - a. Always
 - b. Sometimes
 - c. Never
7. Because of my psoriasis of the nails, I have trouble turning my door key.
 - a. Always
 - b. Sometimes
 - c. Never
8. Because of my psoriasis of the nails, I have trouble driving my car.
 - a. Always
 - b. Sometimes
 - c. Never
9. Because of my psoriasis of the nails, someone helps me to get dressed.
 - a. Always
 - b. Sometimes
 - c. Never
10. Because of my psoriasis of the nails, I avoid doing big jobs around the house:

- a. Always
- b. Sometimes
- c. Never

11. Because of my psoriasis of the nails, I am more irritable than usual, and bad-tempered with people:

- a. Always
- b. Sometimes
- c. Never

Adapted from Ortonne, J.P., et al., *Development and validation of nail psoriasis quality of life scale (NPQ10)*. J Eur Acad Dermatol Venereol, 2010. **24**(1): p. 22-7.
